12.5.2 Overall Best Response Assessment

Each patient will be classified according to his “best response” for the purposes of analysis of treatment effect. Best response is determined from the sequence of the overall response assessments as described in [Section 12.7](#).

12.6 **Response Criteria for Patients with CNS Tumors**

12.6.1 Measurable Disease

Any lesion that is at minimum 10 mm in one dimension on standard MRI or CT, for CNS tumors.

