12.2.4 Response Criteria for Patients with Solid Tumor and Measurable Disease

12.2.4.1 **Evaluation of Target Lesions**

Complete Response (CR): Disappearance of all target and non-target lesions. Any pathological lymph nodes (whether

target or non-target) must have reduction in short axis to <10 mm. If immunocytology is available, no disease must be detected by that methodology. Normalization of urinary catecholamines or other tumor markers if elevated at study enrollment (for patients with neuroblastoma).

Partial Response (PR):

At least a 30% decrease in the sum of the diameters of target lesions, taking as reference the baseline sum diameters

Progressive Disease (PD):

At least a 20% increase in the sum of the diameters of target lesions, taking as reference the smallest sum on study (this includes the baseline sum if that is the smallest on study). In addition to the relative increase of 20%, the sum must also demonstrate an absolute increase of at least 5 mm. (Note: the appearance of one or more new lesions is also considered progressions). Note: in presence of SD or PR in target disease but unequivocal progression in non-target or non-measurable disease, the patient has PD if there is an overall level of substantial worsening in non-target disease such that the overall tumor burden has increased sufficiently to merit discontinuation of therapy

Stable Disease (SD):

Neither sufficient shrinkage to qualify for PR nor sufficient increase to qualify for PD, taking as reference the smallest sum diameters while on study

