12.6.3 Selection of Target and Non-Target Lesions

For most CNS tumors, only one lesion/mass is present and therefore is considered a “target” for measurement/follow up to assess for tumor progression/response. If multiple measurable lesions are present, up to 5 should be selected as “target” lesions. Target lesions should be selected on the basis of size and suitability for accurate repeated measurements. All other lesions will be followed as non-target lesions. The lower size limit of the target lesion(s) should be at least twice the thickness of the slices showing the tumor to decrease the partial volume effect (e.g., 8 mm lesion for a 4 mm slice).

Any change in size of non-target lesions should be noted, though does not need to be measured.

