12.6.4 Response Criteria for Target Lesions

Response criteria are assessed based on the product of the longest diameter and its longest perpendicular diameter. Development of new disease or progression in any established lesions is considered progressive disease, regardless of response in other lesions – e.g., when multiple lesions show opposite responses, the progressive disease takes precedence. Response Criteria for target lesions:

- **Complete Response (CR):** Disappearance of all target lesions.
- **Partial response (PR):** $\geq 50\%$ decrease in the sum of the products of the two perpendicular diameters of all target lesions (up to 5), taking as reference the initial baseline measurements.
- **Stable Disease (SD):** Neither sufficient decrease in the sum of the products of the two perpendicular diameters of all target lesions to qualify for PR, nor sufficient increase in a single target lesion to qualify for PD.

- **Progressive Disease (PD):** 25% or more increase in the sum of the products of the perpendicular diameters of the target lesions, taking as reference the smallest sum of the products observed since the start of treatment, or the appearance of one or more new lesions.

12.6.5 Response Criteria for Non-Target Lesions:

- **Complete Response (CR):** Disappearance of all non-target lesions.
- **Incomplete Response/Stable Disease (IR/SD):** The persistence of one or more non-target lesions.
- **Progressive Disease (PD):** The appearance of one or more new lesions and/or unequivocal progression of existing non-target lesions.

12.6.6 Response criteria for tumor markers (if available):

Tumor markers will be classified simply as being at normal levels or at abnormally high levels.

12.6.7 Overall Response Assessment:

The overall response assessment takes into account response in both target and non-target lesions, the appearance of new lesions and normalization of markers (where applicable), according to the criteria described in the table below. The overall response assessment is shown in the last column, and depends on the assessments of target, non-target, marker and new lesions in the preceding columns.

Target Lesions	Non-target Lesions	Markers	New Lesions	Overall Response
CR	CR	Normal	No	CR
CR	IR/SD	Normal	No	PR
CR	CR, IR/SD	Abnormal	No	PR
PR	CR, IR/SD	Any	No	PR
SD	CR, IR/SD	Any	No	SD
PD	Any	Any	Yes or No	PD
Any	PD	Any	Yes or No	PD
Any	Any	Any	Yes	PD

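### CNS lesions qualify as measurable on one diameter but are scored on the product of two, so in a sole target with a perpendicular diameter of 4 mm or less a 1 mm increase counts as progression

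*Combined protocol and SAP*

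**What the plan says.** All of the following is in the combined protocol and SAP.

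- **Measurability (12.6.1).** A CNS lesion is measurable if it is "Any lesion that is at minimum 10 mm in one dimension on standard MRI or CT, for CNS tumors". Nothing is said about the other diameter.
- **Target selection (12.6.3).** "For most CNS tumors, only one lesion/mass is present", and that lesion is then the target. Where there are several measurable lesions, up to five are chosen on size and on how reliably they can be re-measured. "The lower size limit of the target lesion(s) should be at least twice the thickness of the slices showing the tumor", illustrated by "e.g., 8 mm lesion for a 4 mm slice". The section does not say which diameter this limit governs.
- **Scoring (12.6.4).** "Response criteria are assessed based on the product of the longest diameter and its longest perpendicular diameter". Partial response (PR) is a fall of at least 50% from baseline. PD is a "25% or more increase in the sum of the products of the perpendicular diameters of the target lesions", measured from the smallest sum seen on treatment. The same section adds: "Development of new disease or progression in any established lesions is considered progressive disease, regardless of response in other lesions".
- **Comparison outside the CNS (12.2.4.1).** PD needs a 20% relative increase, and "the sum must also demonstrate an absolute increase of at least 5 mm".
- **What follows from PD.** Protocol therapy ends (5.1 and 10.1). Section 8.2.1 sends CR, PR and stable disease of six or more cycles to central review and does not list PD.

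**The concern.** The entry rule looks at one diameter and the scoring rule multiplies two. The second diameter carries as much weight as the first, yet it may be of any size. When it is small, a small absolute change in it is a large relative change in the product, and only the relative change is tested.

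Most CNS patients are expected to have one target lesion, so the sum of products is usually a single product and nothing dilutes the change. A PD call takes the patient off protocol therapy, ends the stable-disease interval, and under Table 6 in 12.7.1 turns a preceding stable disease, PR or CR into a best response of PD. PD is not among the categories listed for central review, so that review gives no check on it.

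**Working it through.** **Inputs.** Minimum of 10 mm in one dimension (12.6.1); target limit of twice the slice thickness (12.6.3); product of two diameters, PD at +25% or more from the smallest sum, PR at -50% or more from baseline (12.6.4); 5 mm absolute criterion (12.2.4.1). L is the longest diameter and w the perpendicular one.

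**The plan's own figure.** Twice a 4 mm slice is 2 x 4 = 8 mm, as 12.6.3 states. That is below the 10 mm of 12.6.1. Twice the slice thickness exceeds 10 mm only for slices thicker than 5 mm.

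**1 mm of growth in the perpendicular diameter alone.** Relative change = L(w+1)/(Lw) - 1 = 1/w, whatever L is. PD requires 1/w >= 0.25, so w <= 4 mm.

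| Before (mm) | After (mm) | Product (mm²) | Change | PD? |
|---|---|---|---|---|
| 10 x 3 | 10 x 4 | 30 to 40 | +33.3% | yes |
| 10 x 4 | 10 x 5 | 40 to 50 | +25.0% | yes, at the threshold |
| 10 x 5 | 10 x 6 | 50 to 60 | +20.0% | no |
| 10 x 10 | 10 x 11 | 100 to 110 | +10.0% | no |

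1 mm in the longest diameter alone is not PD: 10 to 11 mm is +10.0%.

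**1 mm of growth in both diameters, L = 10.** Relative change = 11(w+1)/(10w) - 1.
- w = 7: 88/70 - 1 = +25.7%, PD.
- w = 8: 99/80 - 1 = +23.8%, not PD.
- w = 10: 121/100 - 1 = +21.0%, not PD.

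**A second target lesion.** With an unchanged 10 x 10 mm lesion, 10 x 4 to 10 x 5 mm moves the sum from 140 to 150 mm², +7.1%, not PD on the sum rule. Section 12.6.4 also makes progression in any established lesion PD, and its stable-disease definition refers to growth in a single target lesion. It is therefore not clear that the sum rule alone decides.

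**If the slice rule covers both diameters.** The smallest allowed w is twice the slice thickness.
- 2 mm slice: w = 4 mm, 1 mm is +25.0%, PD.
- 2.5 mm slice: w = 5 mm, +20.0%, not PD.
- 4 mm slice: w = 8 mm, +12.5%, not PD.

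On that reading a 1 mm PD through the perpendicular diameter is possible only with slices of 2 mm or less.

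**Contrast with 12.2.4.1.** A sole 10 mm target outside the CNS that grows by 1 mm is +10% and falls short of both the 20% and the 5 mm requirement.

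**After a response.** Take 10 x 10 to 10 x 4 to 10 x 5 mm, that is 100, 40 and 50 mm². The last step is +25% from the smallest value, so PD, although the product is still half of baseline. A minimum applied at baseline does not prevent this.

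**The case against.** A reader might infer more than the documents support.

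- **That 8 mm is a rival definition of measurable disease.** It is not. Section 12.6.3 draws targets from lesions already measurable under 12.6.1, so the two limits can be read as cumulative, with 8 mm merely illustrating a ratio. This stands. The example still sits below the 10 mm minimum and should be aligned with it.
- **That any thin lesion is affected.** The slice rule names no dimension and may already limit the short axis, and target selection asks for reproducible measurement. This stands in part. Read generously, the slice rule still admits a 4 mm perpendicular diameter at a 2 mm slice, and selection on reproducibility protects little when there is only one candidate.
- **That false PR is an equal problem.** A 10 x 4 mm lesion read as 10 x 2 mm does fall by 50%. But CR and PR go to central review (8.2.1), the responder definition in 12.2.1.1 requires central confirmation, disease evaluation is repeated in the next cycle (8.1), and Table 6 needs a second assessment. One stray reading does not make a best response of PR. This stands.
- **That CNS response data are largely measurement noise.** The documents give no reader variation, no slice thickness in use and no count of thin CNS lesions. That claim cannot be supported.
- **That the trial's main conclusions are at risk.** Antitumor activity is a secondary aim (1.2.1) and is reported descriptively (11.5). MTD, DLT and PK do not use section 12.6.

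**Conclusion.** The mismatch between 12.6.1 and 12.6.4 is real, and its consequence is limited to PD. In a sole or dominant CNS target with a perpendicular diameter of 4 mm or less, 1 mm of growth in that diameter alone is scored as PD. At 5 mm it is not. If a 10 mm lesion grows by 1 mm in both directions, the limit is a perpendicular diameter of 7 mm.

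This rests on the slice rule not governing the short axis, or on slices of 2 mm or less if it does, and on the growth being counted from the smallest sum on treatment. What is exposed is the PD call and what depends on it in CNS patients: duration of stable disease, best response through Table 6, and time on treatment. How many patients this concerns cannot be told from the documents. It is worth correcting because the correction is cheap and central review does not cover PD.

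**What to change.** 1. In 12.6.1 and 12.6.3, state that the size minimum (10 mm and at least twice the slice thickness) applies to both perpendicular diameters of a CNS target lesion. From 10 x 10 mm, PD through one diameter then needs 2.5 mm (10 x 12.5 = 125 mm², +25%), and 1 mm in both is +21%.
2. Align the 8 mm example in 12.6.3 with the 10 mm minimum.
3. Amend 12.6.2 so that a lesion meeting the minimum in only one dimension counts as evaluable. As worded, 12.6.2 covers only patients with no lesion measurable in even one dimension, so a sole 10 x 4 mm lesion would be neither measurable nor evaluable. Section 4.1.3 requires one or the other, and eligibility criteria cannot be waived (4.0). State that eligibility under 4.1.3 is unchanged.
4. Apply the change prospectively. For CNS patients already enrolled, keep the recorded classification and add a sensitivity listing from the diameters on file.
5. The sponsor should reconcile the absence of an absolute-increase criterion in 12.6.4 with the 5 mm criterion in 12.2.4.1, because item 1 does not protect a lesion that shrinks first. The sum rule and the any-lesion wording in 12.6.4 should be reconciled at the same time.

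The cost is wording in three or four subsections and one data listing, with no new scans. The downside is that thin lesions lose target status and cannot score PR.

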12.6.2 Evaluable Disease

Evaluable disease is defined as at least one lesion, with no lesion that can be accurately measured in at least one dimension. Such lesions may be evaluable by nuclear medicine techniques, immunocytochemistry techniques, tumor markers, CSF cytology, or other reliable measures.

12.6.3 Selection of Target and Non-Target Lesions

For most CNS tumors, only one lesion/mass is present and therefore is considered a “target” for measurement/follow up to assess for tumor progression/response. If multiple measurable lesions are present, up to 5 should be selected as “target” lesions. Target lesions should be selected on the basis of size and suitability for accurate repeated measurements. All other lesions will be followed as non-target lesions. The lower size limit of the target lesion(s) should be at least twice the thickness of the slices showing the tumor to decrease the partial volume effect (e.g., 8 mm lesion for a 4 mm slice).

Any change in size of non-target lesions should be noted, though does not need to be measured.

12.6.4 Response Criteria for Target Lesions

Response criteria are assessed based on the product of the longest diameter and its longest perpendicular diameter. Development of new disease or progression in any established lesions is considered progressive disease, regardless of response in other lesions – e.g., when multiple lesions show opposite responses, the progressive disease takes precedence. Response Criteria for target lesions:

- **Complete Response (CR):** Disappearance of all target lesions.
- **Partial response (PR):** $\geq 50\%$ decrease in the sum of the products of the two perpendicular diameters of all target lesions (up to 5), taking as reference the initial baseline measurements.
- **Stable Disease (SD):** Neither sufficient decrease in the sum of the products of the two perpendicular diameters of all target lesions to qualify for PR, nor sufficient increase in a single target lesion to qualify for PD.

- **Progressive Disease (PD):** 25% or more increase in the sum of the products of the perpendicular diameters of the target lesions, taking as reference the smallest sum of the products observed since the start of treatment, or the appearance of one or more new lesions.

12.6.5 Response Criteria for Non-Target Lesions:

- **Complete Response (CR):** Disappearance of all non-target lesions.
- **Incomplete Response/Stable Disease (IR/SD):** The persistence of one or more non-target lesions.
- **Progressive Disease (PD):** The appearance of one or more new lesions and/or unequivocal progression of existing non-target lesions.

12.6.6 Response criteria for tumor markers (if available):

Tumor markers will be classified simply as being at normal levels or at abnormally high levels.

12.6.7 Overall Response Assessment:

The overall response assessment takes into account response in both target and non-target lesions, the appearance of new lesions and normalization of markers (where applicable), according to the criteria described in the table below. The overall response assessment is shown in the last column, and depends on the assessments of target, non-target, marker and new lesions in the preceding columns.

Target Lesions	Non-target Lesions	Markers	New Lesions	Overall Response
CR	CR	Normal	No	CR
CR	IR/SD	Normal	No	PR
CR	CR, IR/SD	Abnormal	No	PR
PR	CR, IR/SD	Any	No	PR
SD	CR, IR/SD	Any	No	SD
PD	Any	Any	Yes or No	PD
Any	PD	Any	Yes or No	PD
Any	Any	Any	Yes	PD

Each patient will be classified according to his “best response” for the purposes of analysis of treatment effect. Best response is determined as outlined in [Section 12.7](#) from a sequence of overall response assessments.

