4.2.6 Concomitant Medications

4.2.6.1 Corticosteroids: Patients receiving corticosteroids who have not been on a stable or decreasing dose of corticosteroid for at least 7 days prior to enrollment are not eligible. If used to modify immune adverse events related to prior therapy, ≥ 14 days must have elapsed since last dose of corticosteroid (See [Section 4.1.6.1.d](#)).

4.2.6.2 Investigational Drugs: Patients who are currently receiving another investigational drug are not eligible.

4.2.6.3 Anti-cancer Agents: Patients who are currently receiving other anti-cancer agents are not eligible.

4.2.6.4 Anticonvulsants: Patients must not have received enzyme-inducing anticonvulsants for at least 7 days prior to enrollment (see [Appendix V](#) for a list of enzyme-inducing and non-enzyme-inducing anticonvulsants).

4.2.6.5 Anti-GVHD agents post-transplant:

Patients who are receiving cyclosporine, tacrolimus or other agents to prevent graft-versus-host disease post bone marrow transplant are not eligible for this trial.

4.2.6.6 Patients who are receiving any investigational agent other than pevonidistat, including but not limited to androgens, supraphysiologic doses of corticosteroids, erythropoietin, eltrombopag, or romiplostim.

4.2.7 Drug Interaction:

Patients who have received drugs that are strong inducers of CYP3A4 within 14 days prior to study enrollment are not eligible. See [Appendix VII](#) for more details.

While on study, concomitant use of strong CYP3A4 inhibitors (see [Appendix VII](#)), BCRP inhibitors (cyclosporine, eltrombopag, gefitinib), and UGT1A1 inhibitors (diclofenac, ketoconazole, probenecid, silybin, nilotinib, and atazanavir) should be avoided because of potential for increased irinotecan toxicity.

4.2.8 Infection: Patients who have an uncontrolled infection are not eligible.

4.2.9 Patients who have received a prior solid organ transplantation are not eligible.

4.2.10 Patients with known human immunodeficiency virus (HIV) seropositive are not eligible.

4.2.11 Patients with known hepatitis B surface antigen seropositive or known or suspected active hepatitis C infection are not eligible. **NOTE:** Patients who have isolated positive hepatitis B core antibody (i.e., in the setting of negative hepatitis B surface antigen and negative hepatitis B surface antibody) must have an undetectable hepatitis B viral load. Patients who have positive hepatitis C antibody may be included if they have an undetectable hepatitis C viral load.

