7.2 Investigational Agents

No other investigational agents may be given while the patient is on study.

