7.5 Concomitant Medications

Strong CYP3A4 inducers (see [Appendix VII](#)) are prohibited for the duration of the study. Strong inducers of CYP3A4 should be discontinued within 14 days prior to the first dose of pevonedistat.

Concomitant use of strong inhibitors of CYP3A4 (see [Appendix VII](#)), UGT1A1 inhibitors (such as diclofenac, ketoconazole, probenecid, silibinin, tacolimus, nilotinib, and atazanavir), and BCRP inhibitors (cyclosporine, eltrombopag, gefitinib) also should be avoided because of potential for increased irinotecan toxicity.

Acetaminophen may be used judiciously but should not exceed a dose of 37 mg/kg/day (maximum 2 g in 24 hours).

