12.2.1 Definitions

12.2.1.1 **Evaluable for objective response:** Eligible patients who receive at least one dose of protocol therapy will be considered evaluable for response. Evaluable patients who demonstrate a complete or partial response confirmed by central review before receiving non-protocol anti-cancer therapy will be considered a responder. All other evaluable patients will be considered non-responders.

12.2.1.2 **Evaluable Non-Target Disease Response:** Eligible patients who have lesions present at baseline that are evaluable but do not meet the definitions of measurable disease and have received at least one dose of protocol therapy will be considered evaluable for non-target disease. The response assessment is based on the presence, absence, or unequivocal progression of the lesions.

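### The CNS response criteria take no account of corticosteroid dose and the protocol has no clear on-study steroid rule, so a confirmed shrinkage on a raised dose could be counted as a response

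*Combined protocol and SAP*

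**What the plan says.** **Scoring of CNS response.** Section 12.6.4 sets PR at a fall of 50% or more in the summed diameter products "of all target lesions (up to 5), taking as reference the initial baseline measurements". PD is a rise of 25% or more over the smallest sum since treatment began, or a new lesion. The overall assessment in 12.6.7 "depends on the assessments of target, non-target, marker and new lesions in the preceding columns". In Section 12.7, Table 6 gives a best response of PR when a PR is followed by PR or CR, and of stable disease when a stable first assessment is followed by PR or CR. Under 12.2.1.1, a patient with a complete or partial response "confirmed by central review before receiving non-protocol anti-cancer therapy will be considered a responder".

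**Steroids at entry.** Section 4.2.6.1 excludes "Patients receiving corticosteroids who have not been on a stable or decreasing dose of corticosteroid for at least 7 days prior to enrollment". It sets no dose ceiling. Section 4.2.6.6, on patients receiving investigational agents other than the study drug, describes those agents as "including but not limited to androgens, supraphysiologic doses of corticosteroids" and some further drugs.

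**Steroids on study.** Sections 7.1 to 7.5 never name corticosteroids. Section 7.2 says: "No other investigational agents may be given while the patient is on study". Section 7.3 allows general supportive care as needed. Section 7.5 does limit another supportive drug ("Acetaminophen may be used judiciously but should not exceed a dose of" a stated amount) but is silent on steroids. The dexamethasone footnote in Appendix VII points back to 4.2.6.1, and Appendix VI lists dexamethasone only as a possible interaction with irinotecan.

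**Role of response.** Antitumor activity is a secondary aim (1.2.1). Section 11.5 makes its analysis descriptive and hypothesis-generating.

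**The concern.** The entry rule asks for steroid stability before enrollment, but nothing carries that condition into the assessment of response. If a change in steroid dose can alter the measured size of a CNS lesion, image size then reflects both protocol therapy and steroid dose, and the criteria attribute all of it to protocol therapy. The trial has no control arm, and best response is the classification that 12.6 uses to analyze treatment effect, so each CNS response will be read on its own merits. Section 8.1 lists no steroid-dose record at disease evaluations. Unless the dose is captured elsewhere, a reported CNS response could not be interpreted afterward.

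**Working it through.** The plan gives no figure to reproduce on this point. The check sets the rules side by side and follows one hypothetical patient through them.

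**Assumption.** A higher corticosteroid dose can reduce the measured size of a CNS lesion, and a lower dose can let it increase. The documents neither state nor quantify this.

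**Path to a counted response.**
1. A child with a brain tumor enters on a stable dose, as 4.2.6.1 permits. During Cycle 1 the dose is raised for symptoms.
2. The end-of-Cycle-1 scan (8.1) shows a fall of at least 50% in the summed products, so 12.6.4 gives PR. If both diameters shrink equally, this is 1 − √0.5 = 0.293, or about 29% in each diameter.
3. The end-of-Cycle-2 scan comes one 21-day cycle later if there is no delay. If the dose stays raised and the lesion stays small, this is a second PR, and Table 6 gives a best response of PR.
4. Section 8.2.1 sends images to central review. Nothing in it asks the reviewer to obtain or weigh steroid dose.
5. Section 12.2.1.1 removes responses reached after non-protocol anti-cancer therapy. The protocol does not say whether a steroid given for symptoms falls under that term.

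Every written condition is met, and none refers to steroid dose.

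**Paths that do not lead to a counted response.**
- Stable at the first assessment and PR at the second, after a later dose increase: Table 6 gives stable disease.
- Worsening symptoms judged to be clinical progression: protocol therapy ends under 10.1(a), and footnote 5 in 8.1 lets the investigator skip radiographic confirmation.
- A fall below 50%, or one not sustained at the second scan: no PR.

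**The opposite direction.** Patients may enter on a decreasing dose. PD is measured from the smallest sum, so a fall of fraction x followed by a return to baseline is a rise of 1/(1 − x) − 1. Setting this equal to 0.25 gives x = 0.20. A 20% fall during a higher dose, reversed on taper, would thus meet PD with no net change from baseline.

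**Consistency of the steroid rules.** Section 4.2.6.1 admits patients on steroids at any stable or falling dose. Section 4.2.6.6 groups supraphysiologic doses with investigational agents. Read together with 7.2, that could bar such doses on study, but 7.2 does not name them. Section 4.1.6.1.d refers the reader to 4.2.2.1, which does not appear in the text; the steroid rule is in 4.2.6.1.

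**Scale of one response.** The plan defines no CNS stratum or CNS response rate. Section 11.1 expects at most 48 patients overall (18 + 15 + 15) and an absolute maximum of 56 (18 + 23 + 15). One response is 1/48 = 2.1% or 1/56 = 1.8% of those totals. Among an assumed 6 to 10 CNS patients it would be 1/6 = 17% to 1/10 = 10%. These figures are the weight of a single response, not an estimate of bias.

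**The case against.** The strongest objection is that steroids are not left free on study. Section 4.2.6.6 with 7.2 can be read as barring supraphysiologic doses. A reader might infer from the silence of Section 7 that on-study corticosteroids are unrestricted; the documents do not support that. The agent section for the study drug (9.1) is also blacked out, so nothing can be said about its content. What stands is that the readable rules are unclear and do not fit together. Even a firm restriction would leave the scoring gap, because no response rule says how to treat a PR measured on a raised dose.

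A second objection is that several conditions must be met. A reader might infer that any shrinkage after a steroid increase is scored as a response. It is not: the 50% threshold, a PR already at the first assessment, persistence at the second, and central confirmation are all required. The claim is therefore that such a shrinkage could be counted.

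Third, 8.2.1 does not say that clinical data are withheld from central review, and the CRF packet is a separate document that may already capture concomitant steroids. This stands. The finding is only that no rule in the protocol directs their use.

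Fourth, activity is to be defined only preliminarily, and no decision threshold depends on it. This also stands and limits the consequence.

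**Conclusion.** The point holds as a gap in the endpoint definition. As written, the CNS criteria would accept a confirmed response that coincides with a raised steroid dose, and the protocol has no clear or consistent on-study steroid rule that would prevent the situation. This rests on the assumption that steroid dose can affect measured lesion size.

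The effect is confined to the descriptive secondary aim. Response does not enter the DLT, MTD or dose-escalation rules. Its size cannot be estimated from the documents, since neither the number of CNS patients nor the frequency of steroid increases is given.

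A reader might also infer that the error runs only toward apparent activity. That holds for dose increases, but decreasing doses are allowed at entry, and a taper could hide a response or bring a patient to PD. The net direction is not determined.

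**What to change.** 1. Record the daily corticosteroid dose at baseline and at each CNS disease evaluation, and supply it with the images for central review.
2. State in 12.6.4 and 12.6.7 that CR or PR counts only if the dose at the response scan and at the confirmatory scan is not above the dose at the baseline scan; otherwise the assessment is SD at best.
3. Report each CNS response, and each CNS progression during a taper, with the steroid dose at baseline and at the scans concerned. This covers the direction that the scoring rule does not.
4. The sponsor should reconcile 4.2.6.1, 4.2.6.6 and 7.2, and correct the cross-reference in 4.1.6.1.d. No clinical steroid rule is proposed here; items 1 to 3 change data capture and scoring only.

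The cost is about one data field, unless the CRF packet already holds it, and a sentence in each of the two subsections. The downside is that a few CNS responses may be reclassified as stable disease, including some that protocol therapy produced.
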